#### 11. Methods/ to describe resources used

- AN69 hemofilter: it is a semi-selective, semipermeable membrane with a moderate to low cytokine adsorption capacity, but does not remove endotoxins. This membrane is made of polyacrylonitrile (AN69) with a polyethyleneimine treatment.
- AN69-Oxiris hemofilter: It is a highly selective, semipermeable membrane with enhanced capacity for endotoxin and cytokine adsorption. The aforementioned properties are possible given the larger adsorption surface added to the AN69 standard membrane and the presence of a heparin coating that decreases its thrombogenicity and increases its adsorption capacity.

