## 10. Goals

Primary goal: Change in norepinephrine requirement by at least 0.1 micrograms / kg / min to maintain similar MAP after initiation of CRRT with Oxiris membrane compared to standard AN69 membrane. MAP measurements will be performed hourly and norepinephrine requirement will be recorded at that time.

Exploratory goals:

- Effectiveness of the AN69-Oxiris membrane in reducing interleukin serum levels (IL 6, IL 10, and TNF alpha).

Serum will be taken every 8 hours for its measurement by ELISA method.

- To establish the safety (the same risk infection and bleeding) of using the AN69- Oxiris membrane in patients with AKI and COVID-19 infection who require CRRT.

Gross bleeding events (gastrointestinal or urinary) as well as catheter-associated infection events (criteria according to IDSA) will be recorded.

- Length of stay in UCI among patients who used AN69-Oxiris membrane in compared to the use of a conventional membrane (standard AN-69) in critically ill patients with COVID-19 associated AKI and CRRT requirement.

- To investigate the effect of AN69-Oxiris in reducing 28-day mortality in contrast compared with the effect of a conventional membrane in this population.

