#### Monitoring of interventions

- Blood samples will be drawn, every 8 hours during the 72 hours of treatment, to measure cytokine serum levels (IL-6,IL-10,TNF alfa).
- All renal replacement therapy prescriptions (control and intervention group) will be standardized as follows:
  - o Vascular access: 12 French,double-lumen, a high-flux catheter placed into the internal jugular vein or femoral vein (either right or left-sided)
  - o The dose of CRRT will be set at 30ml/kg/h, using ideal body weight.
  - o CRRT modality: Continuous veno-venous hemodiafiltration
  - o Anticoagulation: Regional citrate anticoagulation will be used (Gambro Prismocitrate 18/2-citrate 18 mmol/L). The goal level of ionized calcium in the circuit will be 0.2-0.4 mmol/L. Initial citrate dose will be determined according to the processed blood volume, maintaining a blood flow of 150mL/min, in close relation to a citrate dose of 2.5-5mmolL. Calculations to determine initial citrate dose will be performed using Adequator mobile application, which is widely available and validated for its use. An intravenous calcium infusion will be used to counteract the citrate effect, via a 17.4% calcium gluconate solution to sustain ionized serum calcium between 1.1-1.29 mmol/L in the arterial line.
  - o The Post-dilution substitution fluid rate will be set at 150mL/h.
  - o The dialysate flow rate will be determined as the remaining fluid obtained using the following formula:  
§  $\text{Dialysate} = \text{Total effluent dose} - (\text{citrate infusion rate} + \text{post-dilution substitution fluid rate} + \text{ultrafiltration rate})$
  - o The ultrafiltration rate will initiate at 100mL/hour the first 4 hours and adjusted in according to the patient clinical status and attending physician judgment.
  - o PrismaB/22 (K+ 4, zero-calcium) will be used as a substitution and dialysate fluid.
- Citrate-based anticoagulation monitoring and dosing will be performed using blood gas analysis of samples drawn from both the circuit and patients, according to institutional protocols previously used (described in supplemental material 1).
- Serum electrolytes will be tracked and adjusted using the institutional protocol, which is described in detail in the supplemental material.
- CRRT membrane will be replaced every 24 hours, regardless of the group.
- CRRT treatments will be performed using Prismaflex or PrismaX machines.

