#### 12. Outcomes

Outcomes:

-Primary outcome: to establish the superiority of treatment with the AN69-Oxiris membrane to sustain a similar MAP with a lower requirement of norepinephrine (at least 0.1 micrograms/kg/min) after 72 hours of treatment initiation, in patients with COVID-19 associated AKI requiring CRRT, compared to the usage of a standard AN69 membrane.

-Secondary outcomes:

- To evaluate the effectiveness of the AN69-Oxiris membrane in reducing interleukin serum levels (IL 6, IL 10, and TNF alpha).
- To demonstrate the advantage of the AN69-Oxiris membrane in decreasing 28-day mortality from the start of CRRT.
- To establish the safety of using the AN69-Oxiris membrane in patients with AKI and COVID-19 infection who require CRRT.
- To examine the efficacy of the AN69-Oxiris membrane in reducing the length of ICU stay compared to the use of a conventional membrane (standard AN-69) in critically ill patients with COVID-19 associated AKI and CRRT requirement.

Variables:

Acute kidney injury. Elevation in serum creatinine or decrease in the urinary output according to what is established in the KDIGO guidelines.

Mean arterial pressure. MAP is considered as the perfusion pressure for organs and, a value greater than 60 mmHg is adequate to maintain perfused the organs of an average person. The mean arterial pressure will be registered, either obtained through a peripheral arterial line (calculated from the area under the curve of the arterial pressure graph) or the non-invasive monitor using the oscillometric method.

Furosemide stress test: This term refers to a furosemide bolus of 1 mg/kg (ideal body weight) with subsequent measurement of urine output after 2 hours. It is considered negative when the urine output during this interval is less than 200 ml.

Safety variables:

\* Clotting of the circuit: it is defined as the presence of clots in the circuit lines and/or filter, which condition rise in the transmembrane, pre-filter, or post-filter pressures, warranting a change of the filter.

\* Allergic reaction: the sudden presence of erythema or rash at any time after starting CRRT treatment.

\* Access bleeding: the occurrence of continuous bleeding at the vascular access insertion site any time after the start of CRRT treatment.

\* Catheter-related bloodstream infection: the presence of any microorganism in blood cultures drawn from catheter's lumen.

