#### 15. Exclusion criteria

1. Chronic kidney disease KDIGO stage 4, 5, or 5D.
2. Next of kin unwilling or patient unwilling to participate.
3. Patients with a life expectancy of fewer than 72 hours according to the attending physician criteria.
4. Patients older than 75 years.
5. Patients with SOFA > 11.
6. Patients with severe liver failure.

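### Only the Oxiris filter is described as heparin-coated, yet platelet count is not a prespecified safety variable and eligibility is silent on heparin intolerance

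*Combined protocol and SAP*

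**What the plan says.** **Membranes.** The second Section 11 (description of resources) attributes to the Oxiris filter "the presence of a heparin coating that decreases its thrombogenicity and increases its adsorption capacity". Of the standard filter it says "This membrane is made of polyacrylonitrile (AN69) with a polyethyleneimine treatment", with no mention of heparin.

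**Circuit.** The monitoring part of Section 11 standardises the prescription in both arms: "Regional citrate anticoagulation will be used", and the filter is changed every 24 hours regardless of group. The intervention lasts 72 hours.

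**Safety aim.** Section 10 lists among its exploratory goals "To establish the safety (the same risk infection and bleeding) of using the AN69- Oxiris membrane". Section 12 repeats the safety aim as a secondary outcome.

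**What is recorded.** Section 10 names "Gross bleeding events (gastrointestinal or urinary) as well as catheter-associated infection events". Section 12 lists four safety variables: circuit clotting; "Allergic reaction: the sudden presence of erythema or rash at any time after starting CRRT treatment"; access bleeding, defined as "the occurrence of continuous bleeding at the vascular access insertion site any time after the start of CRRT treatment"; and catheter-related bloodstream infection. Section 19 collects laboratory tests from the electronic records without listing them.

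**Who may enter.** Section 14 has seven inclusion criteria and Section 15 has six exclusions, the last being "Patients with severe liver failure". None mentions heparin or platelets. Section 18 says that all patients who meet the criteria will be included.

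**The concern.** The device description identifies a component present in one arm only, and the eligibility and safety sections do not follow it up.

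Circuit clotting, which the coating is said to reduce, is a named safety variable, so the coating's expected benefit will be counted. A fall in platelets is a form of heparin intolerance that can occur without bleeding or rash, and it has no named variable, no definition and no by-arm report. Followed as written, the plan could reach a safety conclusion on Oxiris with no platelet comparison. It could also randomise a patient with known heparin intolerance to the coated filter without anyone having decided whether that is acceptable.

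The stakes are patient protection at entry and the completeness of the stated safety objective. The primary outcome, the sample size and the primary analysis are not affected.

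**Working it through.** **1. Number exposed.** Section 13 gives a difference of 0.10 and an SD of 0.10 mcg/kg/min, a two-sided 5% level and 80% power. The standardised difference is 0.10 / 0.10 = 1.0. The two-sample t-test calculation gives 16.7, so 17 per arm and 34 in total, as stated; power at 17 per arm is 80.7%. Inflating for 10% loss gives 34 / 0.90 = 37.8, so 38 against the stated 36. That gap of two patients does not bear on this point. The planned Oxiris arm is 18.

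**2. Coated filters planned.** 72 h / 24 h = 3 filters per patient, and 18 × 3 = 54. This is a nominal figure. Early death or stopping lowers it: if 17 patients complete, it is 17 × 3 = 51 plus whatever the eighteenth received. Filter changes for clotting raise it. It counts exposures and says nothing about risk.

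**3. Sections side by side.**

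| Item | Where it is covered |
|---|---|
| Circuit clotting | Section 12 |
| Access bleeding | Section 12 |
| Gross gastrointestinal or urinary bleeding | Section 10 only; absent from the Section 12 list |
| Skin reaction | Section 12 |
| Platelet count | Not named; possibly among the unlisted laboratory tests of Section 19 |
| Heparin intolerance at entry | Neither Section 14 nor Section 15 |
| Systemic heparin given | Not named as a recorded variable |

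**4. What 18 patients can show.** The documents give no rate for a heparin-specific event, so the rates below are assumptions. The chance of at least one event among 18 patients is 1 − (1 − p)^18:

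| Assumed rate p | Chance of seeing at least one event |
|---|---|
| 0.5% | 8.6% |
| 1% | 16.5% |
| 2% | 30.5% |
| 5% | 60.3% |

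If no event is seen, the one-sided 95% upper limit solves (1 − p)^18 = 0.05, so p = 1 − 0.05^(1/18) = 15.3%. This limit applies to any event type, including the bleeding and infection named in the safety goal.

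**5. What a continuous comparison adds.** Step 1 also shows that, with 17 per arm, a difference of one SD in any roughly normal measure is detected with 80.7% power. A by-arm comparison of platelet values can therefore show a large average shift, although not a rare fall in a single patient. The t-test or Mann-Whitney test in Section 16 already covers it.

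**The case against.** The strongest case on the other side has five parts.

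- **Heparin-type harm is already measured.** Bleeding is the direct anticoagulant-type harm and is recorded in both Sections 10 and 12; rash is a possible sign of hypersensitivity. This stands. A reader might infer that no safety variable captures heparin-related harm, or that such harm goes unmeasured. The documents do not support that. The gap is confined to platelets and to entry.
- **Platelet values may be collected anyway.** Section 19 extracts laboratory tests, and Section 14 requires complete laboratories at entry. This also stands, so it would be wrong to say that platelet events could not be counted. What is missing is a named variable and a commitment to report it by arm.
- **The documents state no heparin harm or contraindication.** Correct. They mention only lower thrombogenicity and greater adsorption, and do not say whether the coating releases heparin. The supplement on citrate monitoring is not in the text supplied, and the consent pages were removed, so nothing can be inferred from their absence. The point therefore assumes only that heparin intolerance, including a fall in platelets, is a recognised possibility. It does not assert a contraindication or a rate.
- **Attribution would be weak.** Section 11 leaves other treatment to the attending physician, so systemic heparin may be given in either arm. This is a reason to record it alongside the platelet values.
- **Eighteen patients are too few to detect a rare event.** Step 4 of the working agrees. That limits what the comparison can conclude, but it does not justify omitting it, and it gives more weight to settling the matter at entry.

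**Conclusion.** The point holds in a limited form. The protocol describes heparin in one arm's filter only, records bleeding and skin reactions, does not prespecify platelet count, and does not address heparin intolerance in eligibility. This is an omission between sections, not a contradiction.

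Its size is 18 planned Oxiris patients and 54 coated filters if all complete 72 h. A reader might take 54 as a minimum, but early death or stopping would reduce it. With no events in 18 patients, the data would remain compatible with a true rate of up to about 15%. Even with the fix, the trial can report safety observations but cannot establish safety or equality of risk.

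The conclusion rests on the device descriptions as given, on the standard filter carrying no heparin because none is mentioned, and on full completion of the planned filter schedule. It is a worthwhile, low-cost improvement to patient protection and to the safety objective, and does not threaten the primary result.

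**What to change.** 1. **Section 12, safety variables.** Add platelet count, taken from the laboratory records already collected under Section 19. Report baseline, lowest value and change by arm, together with any systemic heparin given. The investigators should fix any threshold and observation window before data are reviewed; the documents supply neither, and none is proposed here.
2. **Sections 14 and 15 against the device description in Section 11.** Reconcile these so that the sponsor decides and states, before randomisation and identically for both arms, how patients with known heparin intolerance are handled.
3. **Sections 10 and 12.** Align the bleeding variables: gross gastrointestinal or urinary bleeding appears only in Section 10, and access bleeding only in Section 12.
4. **Reporting.** Give safety results by arm with confidence limits, and state that 18 patients with no event leave an upper limit of about 15%.

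The cost is a little extra data entry and possibly a very few patients lost at screening. No new sampling is required if platelet counts are in the routine records, and no new statistical method is needed.

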#### 12. Outcomes

Outcomes:

-Primary outcome: to establish the superiority of treatment with the AN69-Oxiris membrane to sustain a similar MAP with a lower requirement of norepinephrine (at least 0.1 micrograms/kg/min) after 72 hours of treatment initiation, in patients with COVID-19 associated AKI requiring CRRT, compared to the usage of a standard AN69 membrane.

-Secondary outcomes:

- To evaluate the effectiveness of the AN69-Oxiris membrane in reducing interleukin serum levels (IL 6, IL 10, and TNF alpha).
- To demonstrate the advantage of the AN69-Oxiris membrane in decreasing 28-day mortality from the start of CRRT.
- To establish the safety of using the AN69-Oxiris membrane in patients with AKI and COVID-19 infection who require CRRT.
- To examine the efficacy of the AN69-Oxiris membrane in reducing the length of ICU stay compared to the use of a conventional membrane (standard AN-69) in critically ill patients with COVID-19 associated AKI and CRRT requirement.

Variables:

Acute kidney injury. Elevation in serum creatinine or decrease in the urinary output according to what is established in the KDIGO guidelines.

Mean arterial pressure. MAP is considered as the perfusion pressure for organs and, a value greater than 60 mmHg is adequate to maintain perfused the organs of an average person. The mean arterial pressure will be registered, either obtained through a peripheral arterial line (calculated from the area under the curve of the arterial pressure graph) or the non-invasive monitor using the oscillometric method.

Furosemide stress test: This term refers to a furosemide bolus of 1 mg/kg (ideal body weight) with subsequent measurement of urine output after 2 hours. It is considered negative when the urine output during this interval is less than 200 ml.

Safety variables:

\* Clotting of the circuit: it is defined as the presence of clots in the circuit lines and/or filter, which condition rise in the transmembrane, pre-filter, or post-filter pressures, warranting a change of the filter.

\* Allergic reaction: the sudden presence of erythema or rash at any time after starting CRRT treatment.

\* Access bleeding: the occurrence of continuous bleeding at the vascular access insertion site any time after the start of CRRT treatment.

\* Catheter-related bloodstream infection: the presence of any microorganism in blood cultures drawn from catheter's lumen.

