## 11. Methods

Study design: A randomized, multicentric, open-label, controlled trial

Study population: Critically ill patients on mechanical ventilation with AKI and CRRT requirements admitted with COVID-19 disease in any of the two participant institutions.

Participating institutions: INCMNSZ , INER

Timing: October 02th, 2020 to December 30th, 2021.

Interventions: patients meeting inclusion criteria and accepting to participate in this study with informed consent (or legal representative via phone call giving the pandemic lockdown), will be randomized to be treated with CRRT using the AN-69 Oxiris membrane or standard AN-69

membrane (Figure 1). Randomization will be performed on the day of admission using online software (EPIDAT 4.2). The intervention will be sustained during 72 continuous hours.

Patients will be randomized to use one of the following membranes (Figure 1):

CRRT using the AN69 Oxiris membrane (intervention group)

CRRT using the standard AN69 membrane (control group)

\*\*\*Given the pandemic lockdown, informed consents for hemodialysis treatment have been collected by phone call. The study protocol and therapeutic options will be presented to the next of kin; in case of approval for study entry, the date and hour will be registered and a formal appointment for signing the informed consent will be scheduled.

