#### 16. Statistical analysis

Descriptive statistics will be used with measures of central tendency and dispersion of the data according to their distribution. The distribution of the variables will be analyzed with the Kolmogorov-Smirnov "Z" test. For categorical variables, frequencies and percentages will be used. For continuous variables with normal distribution, the mean and standard deviation will be shown. In contrast, the median and interquartile range will be used for continuous variables with an abnormal distribution.

The Student's t-test will be used to compare continuous variables between the two groups, in case of a normal distribution. The Mann-Whitney U-test will be performed for groups with an abnormal distribution. The analysis of data inside the same group at different time intervals (baseline vs 72 h) will be carried out using the Student's t-test, Wilcoxon sum of ranks, or McNemar's test, as appropriate.

Multivariate analysis for mortality will be performed using Cox proportional hazards, adjusted for the baseline SOFA score. Statistical analysis and graphs will be obtained using SPSS 19.0 software (Chicago, IL) and Graphpad Prism 5 software (San Diego, Ca), respectively. A p-value <0.05 will be considered significant. An intention-to-treat analysis will be pursued.

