#### 17. Groups

Group allocation for the AN-69 Oxiris membrane or the standard AN-69 membrane will be done by randomization before starting each CRRT treatment. This process will be performed through Epidat 4.2 software by one of the researchers from the Instituto Nacional de Ciencias Médicas y Nutrición, Salvador Zubirán.

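### 28-day mortality is counted from CRRT start, not from randomisation, so a randomised patient who never starts CRRT has no defined window under the stated intention-to-treat analysis

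*Combined protocol and SAP*

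**What the plan says.** **Mortality.** Section 12 gives the secondary outcome as "To demonstrate the advantage of the AN69-Oxiris membrane in decreasing 28-day mortality from the start of CRRT". Section 10 lists the same outcome as an exploratory goal, with no time origin: "To investigate the effect of AN69-Oxiris in reducing 28-day mortality in contrast compared with the effect of a conventional membrane in this population". Section 16 adds: "Multivariate analysis for mortality will be performed using Cox proportional hazards, adjusted for the baseline SOFA score". It does not state the origin of the Cox time scale.

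**ICU stay.** Section 10 words this goal as "Length of stay in UCI among patients who used AN69-Oxiris membrane", compared with use of the conventional membrane. Section 12 drops the reference to use in the Oxiris arm and describes the population as those "in critically ill patients with COVID-19 associated AKI and CRRT requirement". Neither section says from which day ICU stay is counted.

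**Analysis set.** Section 16 has one sentence: "An intention-to-treat analysis will be pursued". The set is not defined, and nothing is said about patients who are randomised but do not start CRRT.

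**Timing of allocation.** Section 11 (Methods) says: "Randomization will be performed on the day of admission using online software (EPIDAT 4.2". Section 17 says that allocation "will be done by randomization before starting each CRRT treatment". Both put randomisation ahead of connection, and the trial is open-label throughout.

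**The concern.** An intention-to-treat comparison needs a time origin that every randomised patient has and that cannot depend on the arm. Randomisation meets that condition. CRRT start does not: it happens after allocation, some patients may never reach it, and staff who know the arm decide whether and when it happens.

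Three things follow if the Section 12 rule is applied literally. A patient who dies, recovers or has CRRT withheld before connection has no 28-day window. A death between allocation and connection is not counted. If the delay to connection differs between arms, the 28-day windows cover different stretches of time since randomisation.

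The Section 10 wording of ICU stay raises a related problem of population: patients who used a membrane are an as-treated group, not a randomised one. With 18 patients per arm, one or two unassigned patients are visible in the estimate, and a rule chosen after open-label data have been seen would be hard to defend.

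**Working it through.** The documents give no figure for mortality or ICU stay, so the check is mainly one of text. The arithmetic only shows scale.

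**1. The denominator.** Section 13 uses a difference of 0.10 and an SD of 0.10 micrograms/kg/min, two-sided 5% and 80% power. The normal approximation gives 2 × (1.96 + 0.84)² × (0.10/0.10)² = 15.7, so 16 per arm. The t-test calculation gives 16.7, so 17 per arm, as stated. Section 13 then plans 18 per arm after a 10% loss allowance. (17/0.9 = 18.9 would round to 19; that does not affect this point.) The figure of 18 per arm is used below. Moving the mortality origin does not change it.

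**2. Order of events.** Reading Section 17 as one allocation per patient:

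- Under Section 11: day of admission → randomisation → (gap of unstated length) → CRRT start → 28-day clock.
- Under Section 17: decision to treat → randomisation → (probably short gap) → CRRT start → 28-day clock.

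In both, the clock opens after allocation. The gap, and so the chance of a non-starter, is larger under Section 11 than under Section 17.

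**3. Can a randomised patient fail to start?** Section 14 requires KDIGO stage 2 AKI with a failed furosemide stress test, ventilation and a vasopressor. Starting CRRT is not a listed criterion. Sections 7 and 18 limit entry to patients who meet criteria for, or require, CRRT. Section 15 excludes those expected to live less than 72 hours and those with SOFA above 11. These limits make non-starters less likely but do not rule them out.

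**4. Scale.** One patient is 1/18 = 5.6% of an arm. For illustration, assume 9 deaths among 18 randomised (50%) and leave k non-starters out of that arm. The arm's risk then lies between (9 − k)/(18 − k), if all of those left out died, and 9/(18 − k), if none did:

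| k | Lowest | Highest |
|---|---|---|
| 1 | 8/17 = 47.1% | 9/17 = 52.9% |
| 2 | 7/16 = 43.75% | 9/16 = 56.25% |
| 3 | 6/15 = 40.0% | 9/15 = 60.0% |

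With k = 2 and other assumed death counts: 5 deaths (27.8%) gives 3/16 = 18.75% to 5/16 = 31.25%; 13 deaths (72.2%) gives 11/16 = 68.75% to 13/16 = 81.25%.

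The death counts and k are assumptions. For reference, the 10% loss allowance is 0.1 × 18 = 1.8 patients per arm, but Section 13 does not say that these losses are non-starters.

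**5. The primary outcome.** Section 12 places it 72 hours after treatment initiation, and Section 13 places it 72 hours after CRRT initiation. The same undefined case exists there.

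**The case against.** The strongest reply is that nothing here is a stated exclusion. A reader might infer that the plan drops non-starters, contrary to its own intention-to-treat statement. The documents do not support that: no sentence removes such patients, and the conflict arises only if some occur. What stands is narrower. The Section 12 rule, applied as written, cannot place such a patient, and Section 16 does not say what to do instead.

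The lack of a time origin also applies only to mortality. The ICU-stay wording in Section 10 restricts the population but sets no clock, and the Section 12 wording is one that a non-starter can satisfy. For ICU stay the points are therefore two unreconciled wordings and a missing start day.

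A reader might also infer that ICU stay is total stay, and that days before randomisation add much noise. The text does not define it as total stay and gives no SD. If admission in Section 11 means ICU admission, there would be almost no such days. No size can be put on this.

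On frequency, entry is restricted to patients requiring CRRT, and both arms receive CRRT under one standardised prescription (Section 11). A decision to start that differs by arm is thus a possibility, not an expectation. On size, a shift of about 6 points from two patients is small beside the standard error of a difference between arms, √(2 × 0.5 × 0.5/18) = 0.167, or 17 points. Both replies are fair and bear on priority. They do not make CRRT start a better origin.

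**Conclusion.** The point holds as a cheap improvement to outcomes that the plan calls secondary in Section 12 and exploratory in Section 10. The mortality clock is tied to a post-randomisation event in an open-label trial, with no rule for patients who never reach that event. ICU stay has two wordings, one of them as-treated, and no start point.

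The effect on results cannot be estimated from the documents. It depends on how many patients are randomised and not connected, which in turn depends on which statement of randomisation timing applies. Each such patient is 5.6% of an arm. The risk ranges shown rest on assumed deaths and assumed non-starters, and can move in either direction. The planned sample size is unaffected.

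It would go too far to say that the plan contradicts intention-to-treat outright, or that the dates needed for the change are already collected: Section 19 lists length of ICU stay but neither a randomisation date nor a death date.

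**What to change.** - Section 12: count 28-day mortality from randomisation. Section 16: state the same origin for the Cox model.
- Section 10: define the ICU-stay comparison by the membrane to which patients were randomised, not the one they used, and count ICU days from randomisation. Align Section 12.
- Section 16: define the intention-to-treat set as all randomised patients, and report by arm the number who did not start CRRT.
- Section 19: add the randomisation date and the death date to the recorded variables.
- Keep mortality from CRRT start as a sensitivity analysis.
- Reconcile Sections 11 and 17 on when randomisation takes place.
- Sections 12 and 13: state how randomised patients who never start CRRT are handled for the primary outcome. Otherwise the gap is closed for the secondary outcomes and left open for the main one.

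The cost is protocol wording and two dates per patient. The one drawback is that the 28-day window will include a short untreated period in both arms; reconciling the randomisation timing will show how long that may be.
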